Neurological events, defined as AEs of any grade of the Nervous System or Psychiatric Disorders System Organ Class, irrespective of attribution, have been seen in patients exposed to flotetuzumab. The most common of these to date were headache and insomnia. Other neurological events, Grade 3 or higher attributable to flotetuzumab, included delirium, encephalopathy, headache, mental status changes, and syncope. These events generally occurred in the clinical setting of IRR/CRS. Events reported in the Nervous System or Psychiatric Disorders System Organ Class to date have generally been mild to moderate in severity in most patients, and were reversible with no long-term clinical sequelae.

Risk of capillary leak syndrome (CLS) has been associated with T-cell redirecting therapy, including chimeric antigen receptor T-cell (CAR-T) and CD3-engaging bispecific antibody-based molecules, and reported for the CD123-directed cytotoxin, tagraxofusp-erzs (Elzonris®). While CLS has not been frequently observed in patients treated with flotetuzumab, a detailed review of recent clinical data across all flotetuzumab studies identified three patients who received flotetuzumab monotherapy that, concomitant with cytokine release syndrome during multi-step lead-in dosing, exhibited rapid weight gain, decreased albumin, and systemic edema suggestive of CLS. Pleural and pericardial effusions were noted in some cases as well. Of note, CLS may not be associated with hemoconcentration in this patient population.

Acute and chronic GVHD are well-described complications following allo-HCT. Furthermore, new onset or worsening acute and chronic GVHD has been reported in as many as 60-70% of patients receiving DLI alone or in combination with chemotherapy for relapsed AML following allo-HCT. The reported severity of both

acute and chronic GVHD in this setting have ranged from mild to severe, with reports of grade 4 and grade 5 toxicity. Flotetuzumab has been studied in AML patients with primary refractory and relapsed disease in the CP-MGD006-01 study. In addition, other T cell redirecting therapies have been used post-allo-HCT without increased GVHD (17). Nevertheless, flotetuzumab has not been evaluated in AML patients with relapsed disease following allo-HCT and the risk of GVHD in this patient population is unknown.

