**Table 2: Response Criteria**

Complete remission (CR)	Bone marrow blasts <5%; absence of circulating blasts and blasts with Auer rods; absence of extramedullary disease; ANC $\geq 1.0 \times 10^9/L$ (1000/ $\mu$ L); platelet count $\geq 100 \times 10^9/L$ (100,000/ $\mu$ L), transfusion independence
CR with incomplete hematologic recovery (CRi)	All CR criteria except for residual neutropenia ( $<1.0 \times 10^9/L$ [1000/ $\mu$ L]) or thrombocytopenia ( $<100 \times 10^9/L$ [100,000/ $\mu$ L])
Morphologic leukemia-free state (MLFS)	Bone marrow blasts <5%; absence of blasts with Auer rods; absence of extramedullary disease; no hematologic recovery required
Partial remission (PR)	All hematologic criteria of CR; decrease of bone marrow blast percentage to 5 to 25%; and decrease of pretreatment bone marrow blast percentage by at least 50%
Stable disease (SD)	Absence of CR, CRi, PR, MLFS; and criteria for PD not met
Progressive disease (PD)	Evidence for an increase in bone marrow blast percentage (>50% over baseline), and/or increase of absolute blast counts in the blood (>50% to $>25 \times 10^9/L$ ) without differentiation syndrome, or new extramedullary disease

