### 5.3 Response Assessments

Bone Marrow Biopsy (BM Bx) will be performed at the following timepoints for disease assessments and correlative assessments:

- Screening/Baseline BM Bx: performed prior to starting on treatment.
- Cycle 1 D14 (+/- 3 days) BM Bx mid-Cycle 1 (correlative assessments only, no disease response assessment, collected at PI's discretion only).
- Cycle 1 D28 (+/- 3 days) BM Bx following completion of Cycle 1.
- Cycle 2 D28 (+/- 3 days) BM Bx following completion of Cycle 2.
- Final BM Bx performed at the time of suspected disease relapse or progression.

Responses will be assessed via IWG Criteria (Table 2).

See Section 7.0 for additional details regarding bone marrow biopsy schedule and correlative assessments.

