### **5.9 Duration of Follow-up**

Patients will be followed at least every 6 months for 2 years or until death, whichever occurs first. Patients removed from study for unacceptable adverse events will be followed until resolution or stabilization of the adverse event. Patients will return to the clinic for routine post-transplant visits during the first 6 months of follow-up. After the first 6 months, patients can be followed either in person via clinic visit or through a phone call or medical records review.

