## 10.0 MEASUREMENT OF EFFECT

Disease activity will be assessed using CBC and peripheral blood cell morphological examination, examination of bone marrow biopsy, and physical examination. For AML, modifications to the Revised Recommendations of the International Working Group for Diagnosis (IWG), Standardization of Response Criteria, Treatment Outcomes, and Reporting Standards for Therapeutic Trials in Acute Myeloid Leukemia will be used. See table below.

Complete remission (CR)	Bone marrow blasts <5%; absence of circulating blasts and blasts with Auer rods; absence of extramedullary disease; ANC $\geq 1.0 \times 10^9/L$ (1000/ $\mu$ L); platelet count $\geq 100 \times 10^9/L$ (100,000/ $\mu$ L), transfusion independence
CR with incomplete hematologic recovery (CRi)	All CR criteria except for residual neutropenia ( $< 1.0 \times 10^9/L$ [1000/ $\mu$ L]) or thrombocytopenia ( $< 100 \times 10^9/L$ [100,000/ $\mu$ L])
Morphologic leukemia-free state (MLFS)	Bone marrow blasts <5%; absence of blasts with Auer rods; absence of extramedullary disease; no hematologic recovery required
Partial remission (PR)	All hematologic criteria of CR; decrease of bone marrow blast percentage to 5 to 25%; and decrease of pretreatment bone marrow blast percentage by at least 50%
Stable disease (SD)	Absence of CR, CRi, PR, MLFS; and criteria for PD not met
Progressive disease (PD)	Evidence for an increase in bone marrow blast percentage (>50% over baseline), and/or increase of absolute blast counts in the blood (>50% to $> 25 \times 10^9/L$ ) without differentiation syndrome, or new extramedullary disease

Time to response (first or best response) will be calculated from the time of first dose of study drug to the time of initial response. Response duration and time to response will be calculated for patients who achieve an objective response. Progression free survival and overall survival will be calculated as the time from the start of the first dose of study drug until the occurrence of disease progression or death from any cause, respectively.

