**11.7 Statistical analyses**

The data will be analyzed in both intent-to-treat (ITT) and per-protocol (PP) approaches. The ITT cohort will include all patients who have received at least one dose of flotetuzumab. The PP cohort will only include evaluable patients. Patients who withdraw before completing Cycle 1 for a reason unrelated to drug toxicity will not be evaluable for the primary objective and will be replaced. The data analyses will be descriptive in nature. Demographic and clinical characteristics of the sample, as well as response to treatment, and loss to follow up will be summarized using descriptive statistics. The CR rate, overall response rate, PR rate, SD rate, morphologic leukemia-free state (MLFS) rate, and AEs that occur during flotetuzumab monotherapy and their 90% confidence intervals will be presented. Rate of CR, overall response rate, PR rate, SSD rate, MLFS rate, and AEs with subsequent treatment will also be documented with exact 90% confidence intervals. Overall survival (OS) and progression-free survival (PFS) will be described using Kaplan-Meier product limit method.

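### As worded in Section 10.0, progression is the only PFS event, so a death without progression does not count

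*Combined protocol and SAP*

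**What the plan says.** The only definition of PFS is in Section 10.0, in a sentence that covers PFS and OS together. "Progression free survival and overall survival will be calculated as the time from the start of the first dose of study drug" sets a common origin. The sentence then ends "until the occurrence of disease progression or death from any cause, respectively".

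Section 11.7 adds only the method: "Overall survival (OS) and progression-free survival (PFS) will be described using Kaplan-Meier product limit method". It gives no event list and no censoring rule. The Protocol Summary, Section 2.0 and Appendix I list PFS as a secondary endpoint without defining it.

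Section 5.5 sets evaluability by endpoint. As far as the table can be read, PFS falls in the group that needs Cycle 1 infusions completed (or stopped for toxicity or progression) together with a C2D28 assessment, or a C1D28 assessment for one-cycle patients. The table is broken in the text available, so this grouping is probable and not certain.

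Table 2, repeated in Section 10.0, defines CR, CRi, MLFS, PR, SD and PD. It has no relapse category. Relapse does appear beside progression as a biopsy trigger in Section 5.3: "Final BM Bx performed at the time of suspected disease relapse or progression".

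**The concern.** PFS is normally read as time to progression or death, whichever comes first. A reader of the trial report would assume that meaning. Under the Section 10.0 wording the curve would show time to progression, with deaths removed as though those patients had simply stopped being observed. The glossary has a separate abbreviation for time to progression, but the trial lists no endpoint under that name.

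An error of this kind works in one direction only: the curve looks better. In a single-arm trial no concurrent arm carries the same distortion, so comparison with PFS defined conventionally elsewhere would mislead. The protocol accepts that deaths without progression can occur. Section 1.2.1 describes GVHD after DLI "with reports of grade 4 and grade 5 toxicity", DLI is permitted in both cycles, and Table 6 has a row for fatal infusion reactions.

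**Working it through.** The plan states no PFS rate, median or event count, so there is no figure to reproduce. The check is textual, followed by the arithmetic of one Kaplan-Meier step.

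**1. Which event belongs to which endpoint.** The Section 10.0 sentence has two subjects in order (PFS, OS) and two events in order (progression, death from any cause), joined by *respectively*. Pairing them gives PFS = progression and OS = death. If both events had been meant for PFS, *respectively* would have no role. None of the Protocol Summary, Section 2.0, Section 5.5, Section 11.7 or Appendix I makes death a PFS event.

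**2. Effect on the curve.** Let n be the number at risk just before one death without progression, with no other event at that time.
- Death counted as an event: the curve is multiplied by (n-1)/n.
- Death censored: the curve is multiplied by 1.
- The patient leaves the risk set either way, so all later factors are the same.
- Ratio of censored to counted, at all later times: n/(n-1).

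| n at risk | n/(n-1) |
|---|---|
| 25 (planned size, Section 11.3) | 25/24 = 1.042 |
| 15 (illustrative) | 15/14 = 1.071 |
| 10 (illustrative) | 10/9 = 1.111 |

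Illustration with several deaths: suppose the first three of 25 patients to leave the risk set died without progression. Counted, the curve is (24/25)(23/24)(22/23) = 22/25 = 0.88. Censored, it is 1.00. The ratio is 25/22 = 1.136. Three is an example and does not come from the documents. The illustration applies to an analysis set that keeps all 25 patients.

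The direction needs no assumption about frequency. Dropping events while the risk sets stay the same removes factors below 1, so the censored curve is never lower than the conventional one. The two are equal if no such death occurs.

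**3. Analysis set.** Section 11.7 defines an ITT cohort (everyone who received any flotetuzumab) and a per-protocol cohort (evaluable patients only). If Section 5.5 does require a Day 28 assessment for PFS, a patient who dies before it is absent from the per-protocol PFS analysis altogether. Correcting Section 10.0 alone would not bring that death back.

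**4. Relapse after response.** Table 2 measures marrow PD against baseline: blasts must exceed 1.5 times the baseline value. Take 40% at baseline, then CR, then 30%, with no blood-blast or extramedullary sign of PD.
- PD limit: 1.5 × 40% = 60%. 30% is below it, so not PD.
- PR range: 5 to 25%. 30% is above it, so not PR.
- CR, CRi and MLFS all need blasts below 5%, so none applies.
- What remains is SD, which Table 2 defines as "Absence of CR, CRi, PR, MLFS; and criteria for PD not met".

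If progression in the PFS definition means Table 2 PD and nothing else, this relapse is not a PFS event.

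**The case against.** The strongest reply is that the authors meant the usual composite and *respectively* is a slip. That may well be so. It does not remove the point: an analyst following the text would not count these deaths, and no other section corrects the reading. It does mean that the remedy is a wording correction and not a change of design.

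A second reply is that the effect could be nil. This stands. Section 1.2.1 says that none of the infusion reactions or CRS events seen with flotetuzumab was life-threatening or fatal. The fatal GVHD it mentions followed DLI alone or with chemotherapy. The Grade 5 row in Table 6 may only complete a grading scale. Such deaths are possible; their frequency is not documented.

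A reader might infer a definite inflation of median PFS. With constant hazards, if a share f of first events were deaths without progression, the median would be inflated by 1/(1-f): 1.11 at f = 10% and 1.67 at f = 40%. Neither the hazards nor f is in the documents, so this range is hypothetical and not a finding.

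A reader might also infer that the plan excludes relapse from PFS. The documents do not say so. Section 10.0 speaks of disease progression without tying it to Table 2 PD, and the Appendix I response table has a single progression-date column in which an investigator could reasonably enter a relapse. That part is an ambiguity to settle and not a demonstrated error.

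**Conclusion.** The point holds as a minor one. As worded, PFS counts progression only, and a death without progression is not an event. Censoring such deaths is an inference, because Section 11.7 gives no rule, but it is the natural result of applying Kaplan-Meier to that definition. Each such death raises every later value by n/(n-1), from 1.042 with 25 at risk to 1.111 with 10 at risk. The total depends on a count that the documents do not give.

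The consequence is confined to one secondary, descriptive endpoint. The CR/CRi endpoint, the sample size, the futility and safety stopping rules and OS do not use PFS, so nothing here supports a reading that the trial's main conclusion is at risk. The relapse question is a secondary clarification. It matters only if progression is read strictly as Table 2 PD.

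**What to change.** 1. **Section 10.0, events.** Define PFS as time from first dose to the earlier of disease progression or death from any cause. Define OS separately as time from first dose to death from any cause.
2. **Section 10.0, censoring.** Censor patients who are alive and event-free at the last date they were documented free of progression. State what counts as that documentation under remote follow-up, since after six months Section 5.9 says "patients can be followed either in person via clinic visit or through a phone call or medical records review".
3. **Analysis set.** Apply this PFS to the ITT cohort of Section 11.7. Reconcile the PFS row in Section 5.5 so that deaths before a C1D28 or C2D28 assessment are not dropped.
4. **Relapse.** State that disease relapse after CR, CRi or MLFS is a PFS event. The team should choose a blast or extramedullary-disease criterion. Loss of blood-count recovery or of transfusion independence should not serve: a fall in platelets with marrow blasts still below 5% can leave a patient in CRi under Table 2.

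**Cost.** A short paragraph in Section 10.0, an edit to Section 5.5, and no new visits. Section 9.0 already has a Death Form and a Progression Form, so the correction for deaths needs no new data. Relapse dating is less secure. Marrow is taken at suspected relapse, but there is no relapse form, and the Response Assessment Form is scheduled only at baseline, C1D28, C2D28 and end of treatment. The team must therefore agree where a relapse date is recorded. The downside is that reported PFS will look slightly less favourable if any such events occur. The change should be made before PFS is analysed, so that the definition is not chosen with the results in view.

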## 11.0 STATISTICAL CONSIDERATIONS

### 11.1 Hypothesis

Flotetuzumab for relapsed AML following allo-HCT will result in improved response rates compared to historical response rates with chemotherapy or HMA monotherapy

### 11.2 Primary Endpoint

The primary endpoint will be efficacy assessed via composite endpoint of CR and CRi (Cycle 1 Day 28 assessment).

Efficacy Endpoint will be defined as a combined endpoint of complete response (CR) and complete response with incomplete hematologic recovery (CRi), per International Working Group criteria (Table 2, and above.)

### 11.3 Sample Size Estimate

Twenty-five evaluable patients will be enrolled for this study. Assuming a single treatment arm compared to historical controls treated with chemotherapy alone or HMA monotherapy using a dichotomous endpoint of CR/CRi vs not CR/CRi (as defined by the Primary Endpoint, as above), based on Simon's Minimax two-stage design, we estimate a sample size of 25 patients would provide 80% power (alpha 0.05) to detect a difference between a 10% CR/CRi rate in historical controls treated with chemotherapy or hypomethylating agents alone (10, 11) compared to 30% CR/CRi rate in the treatment arm (effect size 20%).

### 11.4 Stopping rules for futility

Fifteen patients will be enrolled in the first stage. This cohort will include all patients who have been treated, including those who withdraw from the study. If at least 2 CR/CRi are observed out of the 15 patients, then an additional 10 patients will be enrolled. If 6 or more CR/CRi are observed from this cohort of 15 patients, we would conclude that there is evidence of efficacy to warrant further investigation. There is less than 5% chance to stop the trial at stage 1 if the "true" response is 30% or higher. Conversely, there will be 55% chance to terminate the study early if the true rate is only 10% or less.

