## APPENDIX I: Study-Specific DSM Tables

Protocol Objectives and Subject Evaluability	
Objective	# of patients evaluable for this endpoint to date
Primary	
To evaluate the efficacy of flotetuzumab in post-allo-HCT relapsed AML and MDS following Cycle 1 of flotetuzumab (Cycle 1 Day 28 assessment).	
Secondary	
To evaluate the efficacy of flotetuzumab monotherapy in post-allo-HCT relapsed AML and MDS following Cycle 2 (or following Cycle 1 for patients that receive only one cycle).	CR and CRi at C2D28 = ORR = MLFS = PR = SD = PFS = OS =
To evaluate the safety and tolerability of flotetuzumab +/- DLI in the post-allo-HCT setting	AEs = CRS and neurotoxicity = Acute GVHD = Chronic GVHD =

Interim Analysis and Early Stopping Rules
Does the study design include an interim toxicity analysis? No
Does the study design include an interim futility analysis? Yes
If yes, please insert text describing interim futility analysis from the protocol Fifteen patients will be enrolled in the first stage. This cohort will include patients who withdraw from the study for reasons unrelated to drug toxicity. If at least 2 CR/CRi are observed out of the 15 patients, then an additional 10 patients will be enrolled. If 6 or more CR/CRi are observed at the end of study, we would conclude that there is evidence of efficacy to warrant further investigation. There is less than 5% chance to stop the trial at stage 1 if the “true” response is 30% or higher. Conversely, there will be 55% chance to terminate the study early if the true rate is only 10% or less.
If yes, please provide data from the interim futility analysis when completed:
Are there early stopping rules that outline circumstances under which the study must be suspended or closed? Yes
If yes, please insert text describing early stopping rules from the protocol A Bayesian sequential monitoring rule will be implemented for safety. The stopping rule is defined as $\Pr(\theta > \theta_T   \text{data}) > 0.8$ , where $\theta$ denotes the proportion of toxicities (as defined in Section 11.5) and $\theta_T$ denotes the expected serious toxicity rate for study treatments (set as $\theta_T = 20\%$ for non-GVHD toxicity and 25% for GVHD toxicity). Interval analyses will be performed

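### Section 11.4 applies the final efficacy threshold (6 or more CR/CRi) to the 15 stage-1 patients, where the design needs 6 or more of all 25; the decision population is also unsettled

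*Combined protocol and SAP*

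**What the plan says.** Section 11.3 names a Simon minimax two-stage design for a CR/CRi rate of 10% against 30%, with alpha 0.05, 80% power and 25 patients. It prints no final cutoff.

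Section 11.4 enrols 15 patients in stage 1 and adds 10 if at least 2 respond. It then says: "If 6 or more CR/CRi are observed from this cohort of 15 patients, we would conclude that there is evidence of efficacy". It also states an early-stopping chance below 5% at a true 30% rate and of 55% at 10%.

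Appendix I repeats the paragraph with a different ending: "If 6 or more CR/CRi are observed at the end of study, we would conclude that there is evidence of efficacy".

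On who is counted:

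- Section 11.3: "Twenty-five evaluable patients will be enrolled for this study".
- Section 11.4, stage 1: "This cohort will include all patients who have been treated, including those who withdraw from the study".
- Appendix I, stage 1: "This cohort will include patients who withdraw from the study for reasons unrelated to drug toxicity".
- Section 11.7: "The ITT cohort will include all patients who have received at least one dose of flotetuzumab. The PP cohort will only include evaluable patients". Both analyses are planned and neither is given precedence.
- Section 11.7 again: "Patients who withdraw before completing Cycle 1 for a reason unrelated to drug toxicity will not be evaluable for the primary objective". Those patients are replaced.
- Section 11.8 limits the efficacy analysis to Cycle 1 completers and withdrawals at least possibly related to toxicity.
- Section 5.5 also treats patients who stop for disease progression as evaluable.

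**The concern.** Section 11.4 is the operative text for the trial's go/no-go decision on its primary endpoint. As written, it ties the success threshold to the first 15 patients and says nothing about how the outcomes of the next 10 are used. A trial that continues with 2, 3, 4 or 5 responses has no stated criterion in Section 11. The end-of-study criterion appears only in an appendix reporting form. Section 11.7 does not fill the gap, since it calls the analyses descriptive and gives no decision rule.

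The population question bears on the same decision. Depending on which section is followed, a patient who withdraws for a reason unrelated to toxicity either counts as not CR/CRi or is replaced. For a patient who progresses during Cycle 1 the sections do not agree either. These choices should be fixed before outcomes are known.

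**Working it through.** **Inputs.** p0 = 0.10, p1 = 0.30, alpha 0.05, power 80%, N = 25 (Section 11.3). Stage 1 n1 = 15, continue if X15 ≥ 2, then 10 more (Section 11.4). Sidedness is not stated; a Simon design is one-sided, and that is assumed here.

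**1. Reproducing the plan's figures.** With X15 ~ Bin(15, p) and Y ~ Bin(10, p):

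- Early stopping = P(X15 ≤ 1)
- P(success) = Σ over x = 2 to 15 of P(X15 = x) × P(Y ≥ 6 − x)

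| Quantity | Stated | Computed, 2/15 then 6/25 |
|---|---|---|
| Early stopping at 10% | 55% | 0.2059 + 0.3432 = 0.549 |
| Early stopping at 30% | <5% | 0.0047 + 0.0305 = 0.035 |
| Type I error | 0.05 | 0.0328 |
| Power | 80% | 0.8017 |

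**2. Is 6 of 25 the only fit?** With the same stage 1:

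| Final cutoff | Type I error | Power |
|---|---|---|
| 5 of 25 | 0.0933 | 0.8981 |
| 6 of 25 | 0.0328 | 0.8017 |
| 7 of 25 | 0.0094 | 0.6578 |

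A cutoff of 5 breaks alpha and a cutoff of 7 breaks power. An exhaustive search of two-stage designs with N from 10 to 25 finds 36 that meet both constraints. All have N = 25 and cutoff 6; the one with the smallest expected sample size is 2 of 15, then 6 of 25.

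**3. The threshold as printed.** P(X15 ≥ 6) = 0.0022 at 10% and 0.2784 at 30%. If 6 of 15 were the only route to success, power would be 27.8%.

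**4. Who is left without a verdict, at a true 30% rate:**

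| X15 | P(X15) | P(Y ≥ 6 − X15) | Product |
|---|---|---|---|
| 2 | 0.0916 | 0.3504 | 0.0321 |
| 3 | 0.1700 | 0.6172 | 0.1050 |
| 4 | 0.2186 | 0.8507 | 0.1860 |
| 5 | 0.2061 | 0.9718 | 0.2003 |
| Total (unrounded sum) | 0.6864 | | 0.5233 |

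So 68.6% of trials enter stage 2 with 2 to 5 responses: 52.3% finish with 6 or more of 25, and 0.6864 − 0.5233 = 16.3% with 5 or fewer. As a check, 0.2784 + 0.5233 = 0.8017, the design's power.

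**5. Population, illustration only.** The documents give no withdrawal or early-progression rates, so these ranges are assumptions.

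(a) Suppose w of the first 15 withdraw and count as non-responders, and the rest respond at 30%. Early stopping is P(Bin(15 − w, 0.30) ≤ 1). If they are replaced, the final analysis has 25 evaluable; if exactly 10 more are enrolled, it has 25 treated, of whom 25 − w are evaluable.

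| w | Early stopping | Power, replaced to 25 evaluable | Power, 25 treated in total |
|---|---|---|---|
| 0 | 0.035 | 0.802 | 0.802 |
| 1 | 0.047 | 0.797 | 0.765 |
| 2 | 0.064 | 0.790 | 0.723 |
| 3 | 0.085 | 0.780 | 0.675 |

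The stated bound of less than 5% fails from w = 2. If 30% is instead the rate over all counted patients, the stated figures are unchanged.

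(b) Suppose a fraction q of treated patients progress during Cycle 1 and are replaced, with a true CR/CRi rate of 10% over all treated. The rate among counted patients is 0.10/(1 − q). For q = 0, 0.05, 0.10 and 0.20, type I error is 0.033, 0.041, 0.051 and 0.082.

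**The case against.** The strongest reply is that this is a recoverable slip. Appendix I belongs to the same protocol and carries the coherent wording. The sample size, alpha, power, futility gate and early-stopping figures are all correct. Enrolling 10 more patients makes little sense if only the first 15 decide. Nothing about the stage-1 decision or patient protection changes. All of that stands. It does not remove the error, because a reader must rebuild the design or consult a reporting form to find the success criterion for the primary endpoint.

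A second reply is that 27.8% is not the trial's power, since 11.4 never says that fewer than 6 of 15 is failure. That is fair. The figure shows only that the printed denominator cannot be the one behind the stated 80%. For a trial with 2 to 5 responses at stage 1, Appendix I gives a verdict and 11.4 is silent.

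Third, 11.3 prints no cutoff and Appendix I does not print 25. This is true: 6 of 25 is inferred from the design inputs together with the appendix, though no other cutoff fits.

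Fourth, on populations, 11.4 does name a set for the 15, and 11.3, 11.7, 11.8 and 5.5 point towards an evaluable set for the 25. Section 11.4 and Appendix I also agree that non-toxicity withdrawals count in stage 1. Sections 11.7 and 11.8 speak of withdrawal, which Section 5.8 lists separately from progression, so 11.7 need not require replacement of progressors. These points narrow the secondary issue. What remains is that the two looks use different sets, the precedence of ITT over PP or the reverse is unstated, and 11.8 leaves out progressors whom 5.5 counts.

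**Conclusion.** The concern holds. The efficacy threshold in 11.4 has the wrong denominator; the design in 11.3, read with Appendix I, requires 6 or more of 25. This rests on exact binomial calculation with a one-sided test and the inputs printed in 11.3 and 11.4. The error adds no false-positive risk. Its cost is that 68.6% of trials at a true 30% rate would reach the end of stage 2 with no success rule in Section 11, and most of those (52.3 of the 68.6 percentage points) would meet the intended criterion.

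The secondary point also holds: no single population is named for both the 2-of-15 and 6-of-25 decisions. Its numerical effect cannot be fixed from the documents. It is small if withdrawals are few and replaced, and larger if progressors were replaced, contrary to 5.5.

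The threshold should be corrected before it is applied, since it is the decision criterion for the primary endpoint.

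**What to change.** In Section 11.4, apply the threshold of 6 or more CR/CRi to all 25 patients, stages 1 and 2 combined. State that 5 or fewer of 25 does not meet the efficacy criterion. Use identical text in Appendix I.

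In the same edit:

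- Name one decision population for both the 15 and the 25, and say whether it is the ITT or the PP cohort of 11.7.
- Say whether a withdrawal unrelated to toxicity counts as not CR/CRi or is replaced.
- Reconcile 5.5, where stopping for progression leaves a patient evaluable, with 11.7 and 11.8, which name only drug toxicity.
- Carry the one definition through 5.5, 11.3, 11.4, 11.7, 11.8 and Appendix I.

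The cost is one corrected sentence and a short repeated definition in a protocol amendment. Sample size, the futility rule and the intended power are unchanged.
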